1.2 RATIONALE FOR CURRENT STUDY

Overall Research Hypothesis:

- Dynamic tumour oxygenation monitoring can predict treatment response in chemoradiotherapy for rectal and breast cancer.

Current Research Hypothesis:

- A novel-designed tumour oxygenation monitor, utilising diffuse reflectance spectroscopy, can provide accurate tissue oxygenation assessment in tumour phantom models.

2. STUDY OBJECTIVES

Primary Objective:

- To develop and validate a novel tumour oxygenation monitoring probe which may be used to monitor response to therapies in cancer, using 3D-printed phantoms.

Secondary Objectives:

- Define the correlation between sensor-derived oxygenation measurements and Gold-standard measured oxygenation in 3D-printed tissue phantoms
- Define the spatial resolution of the sensor oxygenation measurements

3. STUDY DESIGN

3.1 Anonymised MRIs

Anonymised MRIs representative of the chosen breast and rectal clinical paradigms will be used to ensure the generalisability of this research.

MRI DICOM files will be provided by Imperial College NHS Trust Department (ICHNT) of Radiology. The raw DICOM files will be anonymised by the Department of Radiology prior to being received by the research team. The research team will never have access to identifiable information of the MRIs. The MRIs will be stored on a password protected encrypted hard drive.

10 Breast MRIs will be identified by [name] (consultant radiologist specialising in breast malignancy at ICHNT) from previous breast multidisciplinary meetings. The MRIs will be segmented by [name] (and verified by [name]) using slicer (slicer.org) open-source software to delineate malignant tissue.

10 Breast MRIs will be identified by [name] (consultant radiologist specialising in gastrointestinal malignancy at ICHNT) from previous GI multidisciplinary meetings. The MRIs will be segmented by [name] (and verified by [name]) using slicer (slicer.org) open-source software to delineate malignant tissue.

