3.2 TOAST++ Simulations

The TOAST++ framework is software which models the diffuse light transport in tissue, which first requires a Finite Element Mesh of the target issue [8]. These meshes will be constructed based upon the requested anonymised MRI segmentations. Optical signals will be simulated for a variety of sensor/probe/implant designs for a range of tissue parameters, based on scattering and absorption values from the literature [9]. These simulations will be used to initially verify the extent of sensitive volume within the tumours, allowing for optimisation of the sensor-detector spacing. Then hypoxic regions will be simulated based on distributions from the literature and any potential candidates from the MRIs. These simulations will demonstrate the sensitivity of the sensor to changes in oxygenation.

3.3 3D-Printing of Phantoms

Prototype sensor designs will be verified in experiments using phantoms with realistic geometry, based on the same meshes of the MRI segmentations used simulations. The tissue phantoms will be 3D printed tissue phantoms will be produced according to the methodology described by *Dempsey et al.* First the tumour segmentations will be converted to 3D surfaces in standard tessellation language (STL) file format. The phantoms will be printed using a Formlabs 3D printer, using resin containing titanium oxide and near-infrared (NIR) dye (Projet 900NP) so as to mimic tissue absorption and scattering properties.

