3.5 Statistical Analysis

The fraction of the volume of the tumour to which the sensor is sensitive will be expressed as a % of the total volume, and the fraction for each tumour will be expressed as a mean+SD summary statistic.

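### Does the lack of a rule for picking the 20 MRIs undercut the generalisability claim in Section 3.1 enough to change the plan?

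*Combined protocol and SAP*

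**What the plan says.** Section 3.1 opens with the claim at issue: "Anonymised MRIs representative of the chosen breast and rectal clinical paradigms will be used to ensure the generalisability of this research". It then gives a single source: "MRI DICOM files will be provided by Imperial College NHS Trust Department (ICHNT) of Radiology". Selection is described once per site. For breast: "10 Breast MRIs will be identified by [name] (consultant radiologist specialising in breast malignancy at ICHNT) from previous breast multidisciplinary meetings". For the gastrointestinal set: "10 Breast MRIs will be identified by [name] (consultant radiologist specialising in gastrointestinal malignancy at ICHNT) from previous GI multidisciplinary meetings". The second role named in each of those paragraphs verifies the segmentation, not the choice of scan.

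Sections 4.1 and 4.2 and the Study Summary set eligibility: MDT patients with pre-treatment scans who went on to neoadjuvant therapy, aged 18 to 99, 10 per site. None of them says how 10 are drawn from a larger eligible pool.

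The scans are used in three places. Section 3.2 builds simulation meshes from them: "These simulations will be used to initially verify the extent of sensitive volume within the tumours, allowing for optimisation of the sensor-detector spacing". Section 3.3 prints "phantoms with realistic geometry, based on the same meshes of the MRI segmentations used simulations". Section 3.5 reports the sensitive volume of each tumour as a percentage of the whole. For the set of tumours it then says that "the fraction for each tumour will be expressed as a mean+SD summary statistic".

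**The concern.** Read as a sampling statement, the opening of Section 3.1 promises something the method does not supply. One person per site identifies the scans, from one trust, with no consecutive or random rule, date window, log of scans passed over, or required spread of tumour size or location.

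Two results could depend on which tumours are picked:

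- **Sensor-detector spacing.** It is optimised on these tumours, and the phantoms reuse the same meshes. No second set of tumours is named, so the plan contains no check on unseen geometry.
- **Sensed fraction.** Tumour volume is its denominator, so a set weighted towards small or large tumours could shift the mean and SD.

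If the published paper then presented those figures as typical of breast and rectal tumours in general, the claim would outrun its basis.

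**Working it through.** **Counts.** From the Study Summary and Sections 3.1 and 4.1: 10 breast + 10 rectal = 20 scans, consistent across the three places once the site label is read correctly (last step below). Supplying trusts: 1. Identifying radiologists: 1 per site. Scans covered by a stated rule for choosing among eligible scans: 0 of 20. The plan derives the figure 20 from no power or precision target, so there is no sample-size calculation to reproduce.

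**What the claim can mean.** Section 3.1 speaks of scans representative of the two chosen clinical paradigms. Section 1.1.3 defines these as neoadjuvant chemoradiotherapy for locally advanced rectal cancer and neoadjuvant therapy for breast cancer. The eligibility criteria restrict the scans to such patients. If the word means typical examples of these settings, the criteria support it. If it means a probability sample, they do not.

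**Which conclusions need a sample.**

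- Section 1.2 limits the current hypothesis to accuracy in tumour phantom models.
- Section 2 lists probe validation, correlation with the gold standard, and spatial resolution. None is a population estimate of sensed fraction.
- The outcome in the Study Summary sets sensor against reference in the phantoms, so it depends little on which eligible tumours supplied the shapes.
- Section 3.5 gives a mean and SD with no interval or test. The fraction is sensed volume ÷ tumour volume × 100, so each tumour's volume has to be computed anyway and is available to report.

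**Would a sampling rule earn the claim?** As an illustration, suppose the 10 scans per site were a true random sample.

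- The 95% half-width for a mean is t(0.975, n−1) ÷ √n, in SD units. This is 0.72 SD at n = 10 and 0.47 SD at n = 20.
- The chance that a tumour type of prevalence p appears at least once among 10 is 1 − (1 − p)^10. The documents give no prevalence. For assumed values of 5%, 10% and 20% it is 40%, 65% and 89%, so such a type would be missed 60%, 35% and 11% of the time.

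Even ideal sampling at this size leaves wide uncertainty and can miss uncommon shapes. It would also describe only one trust.

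**Would consecutive selection be better here?** Taking the latest 10 eligible scans per site removes some discretion, but it may give a narrower spread of sizes than deliberate choice. For tuning sensor-detector spacing, a deliberate spread is a reasonable engineering choice. If skips were allowed and merely logged, much of the discretion would remain. The reuse of the same meshes for simulation and phantom would be unchanged.

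**The label.** The second selection paragraph of Section 3.1 says breast while naming a gastrointestinal radiologist and GI meetings. The Study Summary and Section 4.1 both give 10 rectal scans. This is a clerical slip with one possible reading.

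**The case for a change.** The strongest case for a change is that the claim is the protocol's own and costs little to repair. A few sentences could state how scans are taken, moderate the verb and list tumour volumes, with the same radiologists, lists and 20 scans. The sensed fraction is the only analysis in Section 3.5, and the choice of cases is the plan's only support for carrying the geometry results to other tumours. The varied tissue parameters and literature-based hypoxia patterns in Section 3.2 test robustness, but not to tumour shape.

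Much of this stands. No rule is stated, and the verb is too strong. That discretion is exercised is an inference, since the text says only that scans are identified, but it is a fair one. What does not follow is that the design must change. The only substantive remedy, a fixed selection rule, exchanges breadth of geometry for reduced discretion and adds screening work for Radiology, without making the claim true. The other remedies concern wording and reporting. They alter no scan, phantom, measurement or analysis.

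**Conclusion.** The observation is correct, but no change to the plan is needed. Section 3.1 overstates what 10 scans per site from one trust can show. They support realistic anatomy for the two clinical settings, and that is all the phantom validation requires. Followed as written, the plan still gives a sound comparison of sensor and reference in phantoms.

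The size is small. All 20 scans lack a stated selection rule, but neither the direction nor the amount of any bias can be derived from the documents. Any effect falls on the optimised spacing and on a descriptive mean and SD. How the scans were chosen, and each tumour's volume, are details that competent analysts would give in the paper.

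This rests on two assumptions: that the sensed fraction stays a description of the tumours studied, and that conclusions stay within phantom models as Section 1.2 states. If the spacing or the sensed fraction were later presented as a population value for breast or rectal tumours, the way the scans were chosen would matter and the conclusion here would not carry over.

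### Surrounding normal tissue is not described in the mesh or phantom, so off-tumour signal cannot be seen and sensor spacing is chosen on tumour coverage alone

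*Combined protocol and SAP*

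**What the plan says.** Section 3.1 has the breast and the gastrointestinal scans segmented "using slicer (slicer.org) open-source software to delineate malignant tissue". No other tissue class is named.

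Section 3.2 says of the simulation meshes: "These meshes will be constructed based upon the requested anonymised MRI segmentations". The simulations are meant to "verify the extent of sensitive volume within the tumours, allowing for optimisation of the sensor-detector spacing".

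Section 3.3 describes "phantoms with realistic geometry, based on the same meshes of the MRI segmentations used simulations" and, for printing, says: "First the tumour segmentations will be converted to 3D surfaces in standard tessellation language (STL) file format".

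Section 3.5 contains one statistic: "The fraction of the volume of the tumour to which the sensor is sensitive will be expressed as a % of the total volume", summarised over tumours by mean and SD.

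The current hypothesis in Section 1.2 is confined to tumour phantom models. Section 3.1, however, presents the MRIs as securing generalisability, and Section 3.4 says the experiments will judge whether the design is suitable for monitoring oxygenation in tumours.

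**The concern.** In a patient, light from an implanted or inserted sensor does not stop at the tumour margin. Some of it passes through normal breast or rectal tissue and returns to the detector carrying that tissue's oxygenation. If mesh and phantom both end at the tumour surface, this component does not exist in the study, and no planned output could reveal it. The Section 3.5 fraction has tumour volume as its denominator. The comparison with the benchtop spectrometer puts both devices on the same phantom.

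The practical consequence is for the design decision in Section 3.2. Widening the source-detector spacing covers more tumour, which counts in its favour. It also draws more signal from outside the tumour, which counts for nothing. A spacing chosen this way may be wider than one chosen with both effects in view. A second consequence is that a mesh ending at the tumour surface loses light there, which changes the coverage figure itself.

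**Working it through.** The plan gives no figure to reproduce. The check has two parts: the text, then an illustration in which every physical input is assumed.

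**1. The chain in the text.** Malignant tissue is delineated (3.1); meshes are built from those segmentations (3.2); phantoms use the same meshes, with tumour segmentations converted to surfaces (3.3); the summary is a fraction of tumour volume (3.5). Normal breast, fat, rectal wall and mesorectum appear nowhere in the segmentation, mesh or phantom description. Nothing expressly rules them out.

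**2. Share of sensitivity outside the tumour.** Assumptions: spherical tumour of radius R in optically identical tissue; reduced scattering μs′ = 1/mm; absorption μa = 0.005, 0.01 or 0.02/mm; spacing 5 or 10 mm.

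- Attenuation: k = √[3 μa (μa + μs′)]. For μa = 0.005, k = √(3 × 0.005 × 1.005) = 0.123/mm. For μa = 0.02, k = √(3 × 0.02 × 1.02) = 0.247/mm.
- Sensitivity at a point at distances r1 and r2 from source and detector: S = exp[−k(r1 + r2)] / (r1 r2).
- Off-tumour share: w = 1 − (sum of S inside the sphere) / (sum of S everywhere).

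Results for a central probe, where the range runs from highest to lowest absorption:

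| Radius | Spacing 5 mm | Spacing 10 mm |
|---|---|---|
| 10 mm | 2% to 15% | 6% to 24% |
| 15 mm | 0.2% to 4.5% | 0.5% to 7.5% |
| 20 mm | 0.02% to 1.3% | 0.05% to 2.3% |

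With the probe at the tumour edge the share is 54% to 73% over all three radii, depending on absorption, spacing and orientation. For a central probe, widening the spacing raises w at every radius and absorption. This is the cost that the plan's optimisation does not see.

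**3. What such a share does to a reading.** Under linear mixing, reading = (1 − w) × tumour + w × normal. The bias is w × (normal − tumour), and the response to a change in tumour oxygenation is scaled by 1 − w. Assume 20% saturation in tumour and 70% in normal tissue, a gap of 50 points. At 10 mm radius with a central probe the bias is 0.02 × 50 = 1 to 0.24 × 50 = 12 points, and at the upper end the response is scaled by 0.76. At 20 mm radius the bias is at most about 0.023 × 50 = 1.2 points. An isolated tumour shows no bias and full response.

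**4. Direction for the Section 3.5 statistic.** The percentage of tumour volume sensed was compared between a tumour-only sphere with a fully absorbing surface and the same sphere embedded in tissue. A point counted as sensed if S exceeded a set fraction of its value at the centre; this threshold is also assumed. Settings were central probe, radii 10, 15 and 25 mm, spacing 5, 10 and 15 mm, absorption 0.005 and 0.02/mm, thresholds 1%, 5% and 10%. Examples at 10 mm spacing and the 5% threshold:

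| Radius | Absorption | Tumour-only | Embedded |
|---|---|---|---|
| 10 mm | 0.005/mm | 38.6% | 96.5% |
| 15 mm | 0.005/mm | 21.9% | 31.5% |
| 25 mm | 0.2/cm = 0.02/mm | 3.1% | 3.1% |

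The tumour-only figure was equal or lower in all 3 × 3 × 2 × 3 = 54 comparisons. A fully absorbing surface is an extreme assumption; a partly reflecting one would narrow the gap.

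**The case against.** A reader might infer that leaving out normal tissue overstates sensor performance. The documents and the check do not support that as a general statement. For the one statistic in Section 3.5 the effect is nil or in the opposite direction. For agreement between sensor and benchtop spectrometer, both devices measure the same phantom, so the direction cannot be determined. What may look too good is tumour specificity and responsiveness to oxygenation change, and the plan does not list either as an endpoint in those terms.

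A reader might also infer that surrounding tissue is excluded by construction. The text is silent rather than explicit: meshes are based upon the segmentations, Section 3.2 speaks of "which first requires a Finite Element Mesh of the target issue" (presumably meaning tissue), Figure 3 is not available in the copy reviewed, and the cited phantom method is not reproduced. Tumour-only is nevertheless the natural reading, most clearly for the printed phantoms.

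Two further objections have weight. The off-tumour share is small for a central probe in a large tumour, and the edge figures depend on a probe position that the plan never states. The study is also an early bench stage with a hypothesis confined to phantoms, and implantation is left to later work, so starting with isolated tumours is a legitimate staged choice. The secondary objective on spatial resolution bears on how far the sensor samples, but Section 3.5 attaches no analysis to it.

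What stands is that spacing is a product of this study and would be carried forward. It is chosen on a quantity that ignores off-tumour signal and may itself be distorted by the missing tissue.

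**Conclusion.** The point holds in a limited form and should be addressed. As written, segmentation, mesh and phantom cover malignant tissue only. Off-tumour signal therefore cannot be observed, and spacing is optimised on coverage with no counterweight.

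The size depends on tumour radius and probe position. It is material for small tumours or a probe near the margin (up to about 24% of sensitivity with a central probe at 10 mm radius, over half at the edge) and negligible for a central probe at 20 mm radius (about 2% at most). These figures rest on an assumed uniform diffusion model and assumed optical properties; none comes from the documents.

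The direction differs by outcome: Section 3.5 coverage unchanged or understated, specificity and responsiveness possibly flattered, sensor-versus-benchtop agreement undetermined. A blanket claim of overstated performance should not be made.

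**What to change.** - **Section 3.2:** state which tissues the mesh contains. Grow each tumour mask automatically by a fixed margin (for example 20 mm), give the shell normal-tissue optical properties from the literature source the plan already uses, vary them over a range as a sensitivity analysis, and run TOAST++ on the combined mesh.
- **Section 3.5:** beside the percentage of tumour volume sensed, report the percentage of total sensitivity that lies inside the tumour. State in advance that spacing will be chosen on both.
- **Section 3.4:** because the printed phantoms would remain tumour-only, limit the accuracy conclusion drawn from them to isolated tumour phantoms.

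The cost is one automatic step for each of the 20 scans, larger meshes and longer run time; no extra reader or manual segmentation is needed. A uniform shell is a simplification that ignores the rectal lumen, skin and other real boundaries, so the in-tumour percentage will depend on the model and should be reported as such.

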3.2 TOAST++ Simulations

The TOAST++ framework is software which models the diffuse light transport in tissue, which first requires a Finite Element Mesh of the target issue [8]. These meshes will be constructed based upon the requested anonymised MRI segmentations. Optical signals will be simulated for a variety of sensor/probe/implant designs for a range of tissue parameters, based on scattering and absorption values from the literature [9]. These simulations will be used to initially verify the extent of sensitive volume within the tumours, allowing for optimisation of the sensor-detector spacing. Then hypoxic regions will be simulated based on distributions from the literature and any potential candidates from the MRIs. These simulations will demonstrate the sensitivity of the sensor to changes in oxygenation.

3.3 3D-Printing of Phantoms

Prototype sensor designs will be verified in experiments using phantoms with realistic geometry, based on the same meshes of the MRI segmentations used simulations. The tissue phantoms will be 3D printed tissue phantoms will be produced according to the methodology described by *Dempsey et al.* First the tumour segmentations will be converted to 3D surfaces in standard tessellation language (STL) file format. The phantoms will be printed using a Formlabs 3D printer, using resin containing titanium oxide and near-infrared (NIR) dye (Projet 900NP) so as to mimic tissue absorption and scattering properties.

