3.4 Sensor Measurement Collection

Measurements of oxygenation within the 3D printed phantoms will first be performed using a benchtop spectrometer to provide a “gold standard”. This benchtop system allows for measurements with a high spectral resolution over a broad spectral range, whereas the sensor by necessity is targeted at key wavelengths (Figure 1). The results of these experiments will assess the suitability of the sensor design for monitoring oxygenation in tumours.

[figure not shown]

Figure 3: Schematic demonstrating a 3D printed phantom, TOAST++ simulation, novel monitoring probe and future miniaturised device (left to right)

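### Does choosing the sensor-detector spacing on the same tumour meshes make the reported sensitive-volume fraction too optimistic?

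*Combined protocol and SAP*

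**What the plan says.** Section 3.2 builds finite element meshes from the MRI segmentations and runs light-transport simulations on them: "Optical signals will be simulated for a variety of sensor/probe/implant designs for a range of tissue parameters". The simulations have a first use in fixing the geometry: "These simulations will be used to initially verify the extent of sensitive volume within the tumours, allowing for optimisation of the sensor-detector spacing". Hypoxic regions are simulated after that. Section 3.3 carries the work to printed phantoms: "Prototype sensor designs will be verified in experiments using phantoms with realistic geometry, based on the same meshes of the MRI segmentations" used in the simulations. Section 3.4 closes by assessing a single design: "The results of these experiments will assess the suitability of the sensor design for monitoring oxygenation in tumours".

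Section 3.5 is the whole statistical analysis. It says "The fraction of the volume of the tumour to which the sensor is sensitive will be expressed as a % of the total volume", and that "the fraction for each tumour will be expressed as a mean+SD summary statistic". It names no design, spacing or tissue-parameter setting. The Study Summary gives 20 scans, 10 rectal and 10 breast. Section 3.1 says that MRIs representative of the two cancers "will be used to ensure the generalisability of this research".

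**The concern.** The quantity that guides the choice of spacing appears to be the quantity reported, on the same tumours. If an analyst tries several spacings, keeps the one with the highest mean fraction and reports that mean, the figure includes some luck: the winner is partly the spacing that happened to suit these 20 shapes. The expected error cannot be negative.

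The plan does not say how the spacing is chosen, whether one spacing serves all tumours or one serves each cancer type, which design Section 3.5 describes, or when the design is settled. A reader who took the mean as a forecast for new tumours, encouraged by the generalisability sentence in Section 3.1, might expect slightly wider coverage than the device would give.

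**Working it through.** **What the documents give.** There are 20 tumours (10 per type), more than one design, and a summary by mean and SD. They give no number of candidate spacings, no SD of the fraction, no correlation between spacings and no selection rule, so there is no stated figure to reproduce. Everything below rests on assumptions.

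**Assumptions.** K = 3, 5 or 10 spacings are compared; the one with the largest mean fraction over n tumours is chosen; fractions are roughly normal; one tumour's fractions at two spacings have correlation ρ = 0.8 or 0.95. High correlation is plausible because every spacing is tried on the same tumours. Results are in units of the tumour-to-tumour SD of the fraction.

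**Worst case for each K and ρ: all spacings truly equal.** The part of the error shared by all spacings does not affect the choice, so

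excess = SD × √((1 − ρ)/n) × E[max of K standard normals],

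with E[max] = 0.85, 1.16 and 1.54 for K = 3, 5 and 10.

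- n = 20, ρ = 0.8: √(0.2/20) = 0.10, giving 0.085, 0.116 and 0.154 SD.
- n = 20, ρ = 0.95: √(0.05/20) = 0.05, giving 0.04, 0.06 and 0.08 SD.
- n = 10 (one spacing per cancer type), ρ = 0.8, K = 10: √(0.2/10) × 1.54 = 0.141 × 1.54 = 0.22 SD.

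**Compared with sampling error.** The standard error of the mean is 1/√20 = 0.22 SD for 20 tumours and 1/√10 = 0.32 SD for 10. The ratio of excess to standard error is √(1 − ρ) × E[max], whatever n is. At ρ = 0.8 and K = 10 it is 0.447 × 1.54 = 0.69.

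**Spacings that really differ.** Simulation (40,000 replicates, n = 20, ρ = 0.8), with true means spread over 0, 0.5 or 1 SD, gives:

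| K | spread 0 | spread 0.5 SD | spread 1 SD |
|---|---|---|---|
| 3 | 0.085 | 0.010 | 0.001 |
| 5 | 0.117 | 0.043 | 0.013 |
| 10 | 0.155 | 0.088 | 0.049 |

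The excess shrinks as the choice of spacing matters more.

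**Where the reassurance fails.** For K = 10 and equal spacings, the excess passes one standard error when √(1 − ρ) × 1.54 > 1, that is, when ρ < 1 − (1/1.54)² = 0.58. At ρ = 0 with an assumed SD of 20 percentage points and n = 20, the excess is 6.9 points against a standard error of 4.5.

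**Whether the condition is met.** Section 3.2 ties the spacing to the extent of sensitive volume but does not say that the mean fraction is maximised. If the spacing is set on other grounds, such as signal or fit within the device, this excess is zero. The second quoted clause of Section 3.5 can also be read as a mean and SD for each tumour over the simulated tissue parameters; there is then no single across-tumour mean to inflate.

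**The case for a change.** The best argument for changing the plan does not depend on bias. This fraction is the only statistic that Section 3.5 describes, and with several designs and a range of tissue parameters it is tied to none of them. A table of the mean and SD for every candidate spacing would use simulations that have to be run anyway and would show how far the choice moved the figure.

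The omissions are real: no selection rule is given, and the design and tissue parameters summarised are not named. But this is missing detail, not a wrong method. The source of the figure is fairly clear, since Section 3.2 places sensitive volume in the simulations and Section 3.4 describes only oxygenation measurements in phantoms. The order of work is clear too: spacing, then hypoxic regions, then prototypes in phantoms. Several prototypes leading to one assessed design is normal where the primary objective is to develop as well as validate.

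The possible remedies add little:

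- The table would leave the planned mean and SD as they are.
- The gap between the chosen spacing and the candidate average bounds the optimism only in expectation, and loosely when spacings differ: 0.500 SD against an excess of 0.001 SD at K = 3, spread 1 SD, ρ = 0.8.
- A leave-one-tumour-out estimate had equal or larger root mean squared error in all 18 settings tried at n = 20, for example 0.263 against 0.240 SD at K = 5 with equal spacings and ρ = 0.8.
- Freezing the design before phantom work would not touch a bias that arises in simulation, and could hamper prototype development.

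On generalisability, Section 3.1 speaks of scans representative of two clinical settings and promises no out-of-sample estimate. Printing the phantoms from the simulated meshes lets simulation and experiment be compared on one geometry.

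**Conclusion.** No change is called for. Followed as written, the plan yields a sound descriptive figure for the tumours studied, and a competent analyst would state the spacing, tissue parameters and unit of summary when reporting it. The optimism needs two things that the documents do not establish: a rule that maximises the mean fraction, and a single mean across tumours. If both hold, and spacings correlate at 0.8 or more, it is 0.00 to 0.15 SD for 20 tumours, or up to 0.22 SD if spacing is chosen within each group of 10; either way it is at most about 0.7 of the standard error. Weaker correlation with many near-equal spacings could take it above the standard error, so the conclusion does not rest on size alone. It rests also on what the figure is used for. The outcome measure in the Study Summary is the correlation with the gold standard, the secondary objectives in Section 2 are that correlation and spatial resolution, and no test or threshold uses the fraction. Nothing here implies bias in the correlation.
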